Protocol Title: Early Fortification of Human Milk for Very Low Birth Weight Infants and Effects on Growth Velocity

Principal Investigator: [name], DO

1. Objectives

Describe the purpose, specific aims, and hypothesis:

The purpose of this investigation is to determine whether early fortification of human milk feeds improve growth outcomes for very low birth weight infants (VLBW) (birth weight 1000-1500 grams). We hypothesize that introducing higher caloric feeds at the onset of enteral feeds will improve early growth metrics in VLBW infants as compared to infants who begin human milk fortification after the first week of life, which represents our present standard of care. The primary outcome for this study is growth velocity (g/kg/day) at 28 days of life.

2. Background

Describe the background and rationale for the study:

Human milk, maternal or donor milk, is the standard of care for feeding premature infants. However, human milk alone does not provide sufficient energy, protein, fat, and micronutrients to meet the demands of the VLBW premature infant. Thus, slow growth can persist for preterm infants and catch-up growth can be incomplete even after discharge from the NICU, and slow extra-uterine growth (weight, length, and head circumference) is associated with poor neurodevelopment and lower intelligence in school age children born preterm. Using human milk fortifiers (HMF) increase nutrient density of human milk and allows for infants to maintain a human milk-based diet, which has been shown to reduce the incidence of necrotizing enterocolitis (NEC) and improve cognitive outcomes in preterm infants.

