n= the end of the interval of time chosen

Head Circumference

1. Head circumference will be measured within 24 hours of birth (x 3) and then every 7 days until 28 days of life and again at 36 weeks PMA. Discrepancies of greater than 0.5cm will be repeated.
2. Measurement of head circumference will be performed by the principal investigator (PI) and/or co-Investigators
3. Head circumference will be measured with a Seca® non-stretch, Teflon® measuring tape.
4. The tape will be applied firmly around the head above the supraorbital ridges, covering the most prominent part of the frontal bulge anteriorly, and over the part of the occiput that gives the maximum circumference.
5. The greatest of three measurements will be recorded in centimeters (cm) and average recorded.
6. Measurements will be recorded in the EMR and documented in the database.

Length

1. Body length will be measured within 24 hours of birth (x 2) and then every 7 days until 28 days of life and again at 36 weeks PMA.
2. Length will be measured on a length board with a stationary head piece and adjustable foot piece.
7. Measurement of length will be performed by the principal investigator (PI) and/or co-Investigators
3. One examiner will hold the infant's head with the Frankfurt plane in the vertical position and apply gentle traction to bring the top of the head into contact with the fixed headboard. The second examiner will hold the infant's feet, toes pointing directly upward, and also applying gentle traction to bring the movable footboard to rest firmly against the infant's heels.
4. The average of two measurements, agreeing within 0.4 cm, will be recorded.
5. Measurements will be recorded in the EMR and documented in the database.

Z-scores

1. Z-scores for weight, length, and head circumference will be retrieved from the EMR. Z-scores will be calculated at 28 days of life and 36 weeks PMA.
2. Z-scores are calculated by Cerner® (Cerner®, North Kansas City, MO) and recorded on the Fenton growth curve in the EMR

Mother's Milk Collection

1. Mother's milk collection will follow standard NICU milk collection procedures: All study participants will be provided with:
 - a. Instructions for milk collection, written and verbal
 - b. Access to a hospital grade electric breast pump, individual pump kit, and a comfortable place to express

- c. A manual breast pump will be provided upon request
- d. Sterile, single-use breastmilk collection containers

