- e. Milk collection labels with a unique bar-code generated by the Cerner Bridge® bar-code system

2. All breastmilk will be processed and prepared in the NICU Milk Lab by trained technicians per standard policy and procedure.
3. The Cerner® Bridge label on each container of breastmilk will be scanned and recorded into the Cerner® Bridge breastmilk management system.
4. All containers of mother's milk collected in one 24 hour span of time will be pooled into a single container per standard NICU Milk Lab procedure. Expiration date and times will be adjusted by Cerner® Bridge once each container is scanned and combined.

2. *Describe the procedures performed to lessen the probability or magnitude of risks:*

As the only intervention that deviates from current standard of care is the use of HMF from feeding day 1 to feeding day 7, we do not anticipate any unique risks for study participants in either group. All SOPs for the handling of human milk and bedside feeding will be followed.

3. *Describe the duration of an individual subject's participation in the study and the time involved also include the overall duration of the project:*

Neonates will be enrolled in the study from birth until 36 weeks post-menstrual age or discharge from the NICU, whichever comes first. Estimated time in the study is two to twelve weeks depending on gestational age at birth.

9. Data and Specimen Management

a. Describe the data analysis plan, including any statistical procedures:

All statistical analysis will be performed using SAS 9.4 and statistical significance will be assessed using an alpha level of 0.05. Descriptive statistics within fortification group (day 1 or day 8) will be determined including means and standard deviations for continuous variables, frequencies and percentages for categorical variables, and medians and interquartile ranges for ordinal variables. Distributional assumptions will be examined before testing and if violations to the assumptions occur a transformation or nonparametric methods will be used. Missing data will not be imputed.

N/A

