To examine differences between the two groups and assess for potential confounding variables two-sample t-tests will be used for continuous variables, chi-square tests will be used for categorical variables, and Wilcoxon Rank Sum tests will be used for ordinal data. Variables that will be examined include all collected EMR data (e.g., demographics, feeding related, laboratory, and clinical measures) and anthropometric measures.

To examine differences between the two groups (day 1 vs. day 8), a simple two-sided two-sample t-test will be used as a preliminary test for differences in continuous outcomes (e.g., weight growth velocity, head circumference growth velocity, length growth velocity, zscores). Then, to control for various potential confounders or covariates, analysis of covariance (ANCOVA) will be used with the main effect of interest being the group effect. Covariates that will be adjusted for include gestational age, total number of feed interruptions, incidence of metabolic acidosis, and NEC. Because there are only two groups, no adjustment to the overall alpha level will be needed to control for multiple comparisons.

b. When applicable, provide a power analysis:

N/A

The sample size was determined assuming an alpha level of 0.05, power of 80%, a common standard deviation of 3.64, and a two-sided two-sample t-test to examine differences in weight growth velocity at 28days between the two feeding protocol groups. The mean for the standard of care group (fortification beginning on day 8) was 10.6% and for the intervention group (fortification beginning on day 1) was 12.3, 12.6 and 13.6. The sample size required for each mean difference is below

Assumed Mean in Each Group		Sample Size per Group
Fortification Day 8	Fortification Day 1	
10.56	12.25	74
10.56	12.56	53
10.56	13.56	25

A sample size of 25 per group, for a total of 50 subjects will be needed.

c. Describe how data and specimens will be handled:
 
Data will be collected and recorded on a coded spreadsheet that is stored on a research specific Box drive assigned by AU IRB.
	 N/A

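### Multiplicity is waived because there are only two groups, yet the primary outcome is tested twice at 0.05 with no deciding analysis named, and the secondary tests have no stated status

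*Protocol*

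**What the plan says.** Section 1 names a single primary outcome at a single time: "The primary outcome for this study is growth velocity (g/kg/day) at 28 days of life".

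Section 9a sets one threshold for everything: "statistical significance will be assessed using an alpha level of 0.05". It then gives two analyses of the same outcomes. In the first, "a simple two-sided two-sample t-test will be used as a preliminary test for differences in continuous outcomes"; the examples listed are "e.g., weight growth velocity, head circumference growth velocity, length growth velocity, zscores". In the second, "analysis of covariance (ANCOVA) will be used with the main effect of interest being the group effect". On the adjustment set it says: "Covariates that will be adjusted for include gestational age, total number of feed interruptions, incidence of metabolic acidosis, and NEC". The paragraph closes with the waiver: "Because there are only two groups, no adjustment to the overall alpha level will be needed to control for multiple comparisons".

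The time points are in section 8. Weight gain and weight growth velocity are calculated at 28 days and at 36 weeks PMA. For weight, length and head circumference, "Z-scores will be calculated at 28 days of life and 36 weeks PMA". Sections 4 and 9b base the sample size of 25 per group on a two-sided two-sample t-test of weight growth velocity at 28 days.

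**The concern.** The waiver rests on the number of arms, but multiplicity here does not come from the arms. It has two other sources.

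1. **Two tests of the primary hypothesis.** The t-test is called preliminary, which points to the ANCOVA as the main analysis. The sample size is built on the t-test, which points the other way. If the two disagree at 0.05, the protocol does not say which one answers the primary question. The choice could then be made after both p-values are known.
2. **Several outcomes at two times.** Three growth velocities and three z-scores are tested at the same 0.05. They are not described as secondary or exploratory in section 9a, and the list is open-ended.

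The first source affects the trial's main claim. The second affects only how far a significant result on another outcome can be trusted.

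**Working it through.** **Inputs from the protocol.** Alpha 0.05 two-sided, power 80%, SD 3.64, control mean 10.56, intervention means 12.25, 12.56 and 13.56, 25 per group (sections 4 and 9b); four ANCOVA covariates (section 9a). The protocol gives no covariate R² and no correlation between outcomes, so both are assumptions shown as ranges.

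**Step 1: the plan's own figure.** Solving the noncentral-t power equation for a two-sample t-test at two-sided 0.05 and 80% power:

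| Difference | n per group, solved | Rounded up | Protocol |
|---|---|---|---|
| 12.25 − 10.56 = 1.69 | 73.8 | 74 | 74 |
| 12.56 − 10.56 = 2.00 | 52.97 | 53 | 53 |
| 13.56 − 10.56 = 3.00 | 24.1 | 25 | 25 |

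The table reproduces. The design is sized for one unadjusted t-test at 0.05 (power 81.5% at 25 per group for a difference of 3.00).

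**Step 2: the primary tested twice.** If success were declared when either test gives p < 0.05, the type I error is P(t-test or ANCOVA significant) under no effect. For two independent tests it would be 1 − 0.95² = 0.0975. The two tests share the same data, so the true value is lower. Simulation under the null, 25 per group, normal baseline covariates:

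| Covariates | Assumed R² | Either test significant |
|---|---|---|
| 1 | 0.1 | 6.5% |
| 4 | 0.1 | 7.4% |
| 4 | 0.3 | 7.9% |
| 4 | 0.5 | 8.3% |

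At the extremes with four covariates, R² = 0 gives 6.4% and R² = 0.7 gives 9.0%. Each test alone stays at about 5%, so the excess comes only from leaving the choice open.

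These runs treat all covariates as baseline. Three of the four in the protocol (feed interruptions, metabolic acidosis, NEC) arise after feeding starts. The planned ANCOVA may therefore estimate a different effect from the t-test, which the simulation does not capture.

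**Step 3: counting the growth comparisons.**

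- Fixed by the text: weight growth velocity at 2 times + 3 z-scores × 2 times = 2 + 6 = 8. One of these eight is the primary itself.
- Head circumference and length growth velocity are named, but no calculation time is given. One time each makes 8 + 2 = 10.
- Two times each makes 6 outcomes × 2 = 12. Adding weight gain in g/day at two times to the 10 also gives 12.

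**Step 4: familywise error at 0.05 per test.** If independent, 1 − 0.95^k:

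- k = 8: 0.34
- k = 10: 0.40
- k = 12: 0.46

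With an assumed common correlation, simulated for k = 12: 0.40 at 0.3, 0.32 at 0.5, 0.23 at 0.7, 0.14 at 0.9. For k = 8 to 10 at a correlation of 0.9 it is 0.12 to 0.13. The range over all these settings is about 12% to 46%.

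**Step 5: what a correction would cost instead.** For a difference of 3.00, Bonferroni over 2 tests (alpha 0.025) needs 30 per group, with power 72% at 25. Over 12 tests (alpha 0.05/12 = 0.0042) it needs 43 per group, with power 47% at 25. Naming one deciding analysis needs neither.

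**The case against.** The waiver directly follows the sentence about the ANCOVA group effect. There, multiple comparisons can be read in the narrow sense of pairwise contrasts between group means. On that reading the sentence is true, and it is incomplete rather than wrong. This stands in part: the sentence is correct for pairwise contrasts. But it speaks of the overall alpha level in a plan that tests many outcomes twice, and it gives no other ground. Because the protocol has fixed this rule itself, the point is not merely one left to a SAP.

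A reader might infer that the trial's false-positive rate is 46%. The documents do not support that. One primary outcome at one time is named, and it alone is powered. Testing other outcomes at 0.05 does not change the error rate of the primary test, and no rule says that any significant secondary result makes the trial a success. Growth measures built on the same weights at overlapping times are also likely to be correlated, so the independence figure is an upper value.

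A reader might also infer that at least twelve comparisons are fixed. The text fixes eight; ten or twelve requires assumptions about head and length velocity or the addition of weight gain.

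Nor does the protocol state that either test of the primary may count. Its wording leans towards the ANCOVA. The 6-9% is the error that the open choice permits, not a stated decision rule. What remains is that the deciding test is not named and that the sample size points to the other one.

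**Conclusion.** The concern holds in a limited form. The reason given for waiving adjustment covers only pairwise group contrasts. The weightier consequence is that the primary outcome has two tests at 0.05 and no named deciding analysis. If either could be claimed, the type I error is about 6-9%, assuming 25 per arm, one to four baseline covariates and R² of 0.1 to 0.5.

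The lesser consequence is that the other growth comparisons are tested at 0.05 without a stated status. The familywise error of about 12-46% over 8 to 12 comparisons (correlation 0.9 down to 0) describes that set, not the primary claim. Leaving secondary outcomes unadjusted is acceptable practice once they are labelled as not confirmatory. The plan should be changed, and the change is small.

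**What to change.** Replace the waiver in section 9a with:

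> The only confirmatory test is the group effect on weight growth velocity at 28 days from one pre-specified ANCOVA adjusted for baseline covariates only (e.g., gestational age), two-sided 0.05. The unadjusted t-test is supportive. All other outcomes and the 36-week time point are reported as estimates with 95% confidence intervals, labelled secondary or exploratory, without confirmatory claims.

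This holds alpha at 0.05 for the primary and leaves N at 25 per group.

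It is more than a change of wording. Of the four covariates now named, only gestational age is known at baseline. Feed interruptions, metabolic acidosis and NEC leave the primary model; they may be kept in a supportive analysis. The other cost is that a significant secondary result can no longer be presented as confirmatory. Labelling the remaining outcomes exploratory is one accepted convention among several; what matters is that their status is fixed before the data are seen.

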
Abdominal circumferences will be measured daily. Monitoring for feeding intolerance will be ongoing.
 
c. Describe how the safety information will be collected (e.g., with case report forms, at study visits, by telephone calls with participants).
 
Bedside nursing staff documents abdominal circumferences in patient's charts. Any signs of feeding intolerance is relayed to the primary care team.
 
d. Describe the frequency of data collection, including when safety data collection starts.
 
Abdominal circumferences are measured daily, starting at birth.
 
e. Describe who will review the data.
 
Information will be reviewed by the PI and sub-investigators.
 
f. Describe the frequency or periodicity of review of cumulative data.
 
Data will be reviewed weekly.
 
g. Describe any conditions that trigger an immediate suspension of the research.
 
Developmental of NEC, necrotizing enterocolitis.

11. Withdrawal of Subjects

N/A

a. If applicable, describe anticipated circumstances under which subjects will be withdrawn from the research without their consent.
 
Subjects will be withdrawn from the study should they meet any one of the following criteria:
 
 1. The subject's parent (s) or legal guardian request that the subject be withdrawn from the study. 2. If, in the attending neonatologist's opinion, continuation in the study would be detrimental to the subject's well being 3. If the participant requires supplemental enteral intake from infant formula or additives such as carbohydrate, protein, or fat modulairs, therefore altering the content of the fortified milk beyond the HP HMF. 4. The subject is diagnosed with NEC stage IIb or higher as described by the Bell's stages. 5. The subject is diagnosed with a gastrointestinal perforation. 6. After a subject has been discontinued, he/she will not be allowed to re-enroll in the study. The reason for a subject being discontinued will be documented in the database. 
b. If applicable, describe any procedures for orderly termination.
	
 N/A

---	-------------------------------------

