
c. If applicable, describe procedures that will be followed when subjects withdraw from the research, including partial withdrawal from procedures with continued data collection.
	 N/A
--	---

12. Risks to Subjects

a. List the reasonably foreseeable risks.
 
 1. Physical risks: Minimal risk of feeding intolerance due to early fortification. Feeding intolerance may present as spit up, irritability, or abdominal distention. Possibility of increased risk of developing NEC, an intestinal infection. 2. Psychological risk: no psychological risk 3. Social risk: no social risk 4. Legal risk: no legal risk 5. Parents or legal guardians have no financial risks associated with this study. 6. There will be no financial costs associated with inclusion in this study 	 N/A

b. If applicable, describe any costs that subjects may be responsible for because of participation in the research.
	 N/A

13. Potential Benefits to Subjects

Describe the potential benefits that individual subjects may experience from taking part in the research.

Introducing higher caloric feeds at the onset of enteral feeds can improve growth outcomes for VLBW infants when compared to infants who begin fortification after the first week of life.

14. Confidentiality

Describe the procedures for maintenance of confidentiality.

1. Subjects are at risk of breach of confidentiality. All research team members have undergone confidentiality training (CITI, HIPAA, and PHI) and are aware of the consequences for breach of confidentiality.
2. To protect subject privacy, data folders in use during testing will not contain personal identifiers and forms containing personal identifiers will be kept out of public view.
3. All subjects will be given a unique identifier.
4. Research raw data will be stored on a drive that is password protected, and databases will be stored on the AU IT provided human research drive. Only the PI and the co-investigators will have access to the drive.
5. If an unanticipated research-related event arises, the PI will be immediately informed of the event. If the event requires medical attention, the study physicians will be contacted for decisions regarding further action as needed.

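### Infants are withdrawn from the study, not just from study feeds, for post-randomisation events, with no stated follow-up, so the day-28 comparison is open to selective loss

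*Protocol*

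**What the plan says.** Protocol section 11a opens with "Subjects will be withdrawn from the study should they meet any one of the following criteria". Apart from a parent's request, the listed triggers are:

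- the attending neonatologist's opinion (criterion 2);
- "If the participant requires supplemental enteral intake from infant formula or additives such as carbohydrate, protein, or fat modulairs" (criterion 3), for which the only reason given is that the milk content is altered;
- "The subject is diagnosed with NEC stage IIb or higher as described by the Bell's stages" (criterion 4);
- gastrointestinal perforation (criterion 5).

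Re-enrolment is barred. The one data step attached to withdrawal is "The reason for a subject being discontinued will be documented in the database".

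The form's item 11c asks: "If applicable, describe procedures that will be followed when subjects withdraw from the research, including partial withdrawal from procedures with continued data collection". No procedure is given there.

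Section 9a states "Missing data will not be imputed". Section 12a lists among the physical risks "Possibility of increased risk of developing NEC, an intestinal infection". On duration, section 8 says "Neonates will be enrolled in the study from birth until 36 weeks post-menstrual age or discharge from the NICU, whichever comes first". The primary outcome (section 1) is growth velocity at 28 days of life, and sections 4 and 9b set 25 infants per group.

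**The concern.** Randomisation protects the comparison only if the infants who contribute a day-28 result are the infants who were randomised. Criteria 2 to 5 are all events after randomisation, and each can occur before day 28. If study data end at withdrawal and nothing is imputed, the primary analysis is a complete-case comparison selected on those events.

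Two mechanisms matter, and they pull in opposite directions:

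- **Loss related to growth.** If slow growers are the ones given formula or additives, and there are more of them in the control arm, their removal shrinks a real difference. This link is an inference.
- **Loss related to arm.** If early fortification causes more NEC or intolerance, the intervention arm loses more sick, slow-growing infants, and the difference is inflated. The protocol's own risk section makes this plausible for NEC.

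Withdrawals before day 28 affect the primary outcome. Later ones affect only the 36-week outcomes.

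**Working it through.** **Inputs from the protocol (sections 4 and 9b).** Means 10.56 and 13.56 (difference 3.0), SD σ = 3.64, two-sided alpha 0.05, 80% power, 25 per group. The protocol gives no withdrawal rate, so every loss pattern below is an assumption.

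**1. The plan's own figure.** The exact two-sample t-test needs 24.1 per group, rounded up to 25, so the stated number reproduces. The standard error of the difference is 3.64 × √(2/25) = 1.03.

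**2. Loss unrelated to outcome.** Noncentral-t power for a difference of 3.0:

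| Lost per arm | n per arm | Power |
|---|---|---|
| 0 | 25 | 81.5% |
| 1 | 24 | 79.8% |
| 3 | 22 | 76.1% |
| 5 | 20 | 71.9% |

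**3. Loss related to growth (dilution).** Assume infants with growth velocity below 7 are withdrawn with probability p. With c = (7 − mean)/σ, the loss is pΦ(c) and the retained mean rises by σ·p·φ(c)/(1 − pΦ(c)).

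- Control: c = −0.978, Φ = 0.1640, φ = 0.2473.
- Intervention: c = −1.802, Φ = 0.0358, φ = 0.0786.

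| p | Loss, control vs intervention | Rise, control vs intervention | Remaining difference | Power (simulated) |
|---|---|---|---|---|
| 0.5 | 8.2% vs 1.8% | 0.490 vs 0.146 | 3.0 − 0.490 + 0.146 = 2.66 | about 74% |
| 1.0 | 16.4% vs 3.6% | 1.077 vs 0.297 | 3.0 − 1.077 + 0.297 = 2.22 | about 64% |

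Type I error stays near 5%, because with no true effect both arms lose the same fraction.

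**4. Loss related to arm (inflation).** Assume withdrawn infants average k SD below those retained in their arm. If a fraction q is lost, the retained mean exceeds the full arm mean by q·k·σ. The bias in the difference is therefore (q intervention − q control) × k × 3.64. Type I error is simulated with no true effect.

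| Loss, intervention vs control | k | Bias, g/kg/day | Type I error |
|---|---|---|---|
| 8% vs 8% | 1 or 2 | 0 | about 5% |
| 12% vs 8% | 1 | 0.04 × 3.64 = 0.15 | 5.2% |
| 12% vs 8% | 2 | 0.04 × 7.28 = 0.29 | 5.8% |
| 20% vs 8% | 1 | 0.12 × 3.64 = 0.44 | 6.7% |
| 20% vs 8% | 2 | 0.12 × 7.28 = 0.87 | 11.8% |

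Of 25 infants, 8%, 12% and 20% are 2, 3 and 5. One extra loss in the intervention arm does little; three extra are material if those infants grew clearly worse.

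**The case against.** **Silence is not exclusion.** No sentence says that withdrawn infants' data are discarded, and the N/A boxes in this form are unreliable: 12a is also ticked N/A beside a full list of risks. Consent terms on data use after withdrawal are not visible. This stands in part: the defect is an open risk created by a stated withdrawal rule, not a declared exclusion. The rule still says the infant leaves the study, and nothing says that collection goes on.

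**The weights will be in the chart.** Anthropometry is routine care, so an infant still in the NICU probably has a weight near day 28. That stands, and it makes the remedy cheap. But the protocol does not provide for taking that weight into the study database after withdrawal, and section 8 assigns study weighings to the investigators. An SAP can define an analysis set; it cannot supply data the study did not collect.

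**The magnitudes are assumed.** Correct. The dilution case selects on day-28 growth velocity itself, which is unknown at withdrawal. With the same loss (16.4% vs 3.6%) and a trigger correlated 0.5 or 0.3 with growth velocity, the difference falls only to 3.0 − 0.5 × 0.780 = 2.61 or 3.0 − 0.3 × 0.780 = 2.77. Section 2 says no study has linked fortifier to NEC. Section 10g makes development of NEC a trigger for suspending the research, so a large NEC-driven imbalance sits awkwardly with continued enrolment. NEC is also a collected outcome and an ANCOVA covariate, so some infants with NEC are evidently expected to have growth data, though cases below stage IIb could account for that. These points limit the likely size; they do not close the gap.

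**Safeguards exist.** Personnel are blinded for the first 7 feeding days, the feeding plan is the same in both arms from feeding day 8, and reasons for discontinuation are recorded. None of these supplies a missing day-28 weight, and blinding does not prevent a true difference in NEC.

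**Conclusion.** The concern holds and should be fixed. Mandatory withdrawal from the study for post-randomisation events, no stated follow-up and no imputation together leave the primary comparison open to selective loss. That reading of the text is secure. The direction and size of any bias are not: they depend on how many infants are withdrawn before day 28, in which arm, and how their growth compares with that of the infants retained. Across the patterns examined, the effect runs from none, through a negligible 0.15 g/kg/day, to a planned difference reduced from 3.0 to 2.22 or a spurious gain of 0.87 with type I error of 11.8%. With 25 per group and power of 81.5%, a single random loss in each arm already takes power just below 80%.

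**What to change.** Leave the clinical criteria in 11a as they are, and distinguish discontinuing study feeding from leaving the study.

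- In 11c, state that for criteria 2 to 5 routine chart weight, length, head circumference and clinical outcomes continue to be collected to day 28 and to 36 weeks PMA or discharge, unless the parent withdraws permission. Match the consent form to this.
- Make the primary analysis all randomised infants in their assigned group, with a per-protocol analysis as secondary.
- Report deaths before day 28 by arm, and add a sensitivity analysis for day-28 outcomes that are still missing.
- Reconcile the passages on NEC: withdrawal trigger (11a), suspension trigger (10g), collected outcome (section 8) and covariate (9a).

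The cost is protocol and consent wording, since the measurements are already standard care. Including discontinued infants may make the primary outcome somewhat more variable.

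An allowance for loss is a separate matter of power: 25/0.90 rounds up to 28 per group and 25/0.80 to 32, that is 3 to 7 more infants per group. It would not remove selection.
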